5.1.1 General study level definitions

5.1.1.1 Analysis Time Points

All data will be analyzed based on the visits identified per the Schedule of Activities in the protocol. Mapping to analysis visit windows is not applied, except for early termination visits (specified in Section 5.1.1.1.4).

5.1.1.1.1 Relative day

Relative day will be provided in different listings and will be calculated as follows:

- If the start (stop) date occurred on or after the first dose, but prior to the drug stop date, relative day is calculated as start (stop) date minus first dose date + 1 (the day of first dose will be Day 1).
- If the start (stop) date occurred before the first dose, the relative day is calculated as date of first dose of investigational medicinal product (IMP) minus the start (stop) date (the day prior to first dose will be Day -1)
- If the start (stop) date occurred after the last dose of IMP, the relative day to the most recent dose is calculated as start (stop) date minus last dose of investigational medicinal product (IMP) including a '+' to denote post treatment days (e.g. the day after last dose will be Day +1).

Relative day will only be computed for fully completed dates and will be missing for partial dates. In such cases, relative day should be presented as ' - ' in the participant data listings. Relative day will be calculated from first dose of IMP

5.1.1.1.2 End date of the Treatment Periods

Each of the study periods is constituted of a treatment period.

The end date of the treatment period of each study period will be either the date of the last planned visit (Week 12 for the Main Treatment Period or the every 12 Weeks visit for the Extension Treatment Period) or the date of the Withdrawal visit (Early Withdrawal during the Main Treatment Period or Withdrawal Visit during the Extension Treatment Period) for participants who discontinued. If a participant does not have the last planned visit or Withdrawal visit, then either the date of the last scheduled (on site or phone call visits) or unscheduled visit during the considered period or the date of the last known dose of study drug during the considered period, whichever is later, will define the end date of the Treatment period.

5.1.1.1.3 Study periods

Based on the specific requirements of safety and efficacy analyses, one concept of the definition of periods need to be considered for the study, which will be defined in detail in the section below.

5.1.1.1.3.1 Study periods for safety and efficacy data

- Two study periods are included in this study, the Main Treatment Period and the Extension Treatment Period.

No efficacy data are collected during the Extension Treatment Period thus, for efficacy analyses, only the Main Treatment Period will be considered.

The safety analyses will be performed on the Main Treatment Period as well as on the Overall Treatment Period. The Overall Treatment Period is constituted of the Main Treatment Period and of the Extension Treatment Period. The following definitions for completing study periods will be applied:

- A participant is considered to have completed the Main Treatment Period if he/she completed the Week 12 visit and:
 - Decided to enter the Extension Treatment Period.
 - OR
 - Transitioned to commercially available ZLP directly after the Week 12 visit (no Withdrawal or SFU visit required).
 - OR
 - Decided not to enter the Extension Treatment Period and completed a SFU visit.
- A participant is considered to have completed the study if he/she completed the Main Treatment Period and:
 - Did not enter the Extension Treatment Period.
 - OR
 - Entered the Extension Treatment Period and:
 - withdrew from the Extension Treatment Period, discontinued ZLP, and completed the Withdrawal and SFU Visits.
 - transitioned to commercially available ZLP and completed the Withdrawal Visit. No SFU Visit is required.

The total duration of study participation in the Main Treatment Period for all participants will be up to approximately 20 or 26 weeks, including the following periods:

- Screening Period: 2 to 8 weeks
- Treatment Period: 12-weeks
- SFU Period: 40 days (after the last dose for patients who do not enter the extension period or do not transition to commercially available ZLP directly after the Week 12 visit).

The Extension Treatment Period is constituted of the following periods:

- Treatment period
- SFU period: 40 days, for participants that withdrew from the Extension Treatment Period

The end of the study is defined as the date of the last visit of the last participant in the study.

The following definitions for starting and entering the periods will be applied:

- Treatment period starts with the first day of IMP and ends at the end date of treatment period defined in Section 5.1.1.1.2. All participants in the Safety Set will be considered to have started the Treatment period of the Main Treatment Period.
- Follow-up period starts one day after the end of the Treatment period and ends after the final assessments on the SFU visit.

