## **9.4       Planned safety and other analyses**

### **9.4.1       Safety analyses**

Safety analyses will be performed on the Safety Set.

Adverse events will be coded using the Medical Dictionary for Regulatory Activities. A TEAE is defined as any event that was not present prior to the first administration of study medication or any unresolved event already present before the first administration of study medication that worsens in intensity following exposure to treatment. Incidence rates for TEAEs will be summarized overall, by maximum severity, and by relationship to study medication. Serious AEs will also be summarized.

Laboratory evaluations, physical examinations, and ECG will be presented in listings and summarized over time. In this study, the clinical laboratory, physical examination, and ECG assessments conducted at Screening will be considered the baseline values for evaluating of the other safety endpoints.

A by-participant listing of the C-SSRS questionnaire data will be provided.

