All study participants who complete the Main Treatment Period will have the option to continue ZLP treatment in the Extension Treatment Period after the Week 12 visit. If a study participant withdraws from the study during the Main Treatment Period, the participant will complete an Early Withdrawal (EW) Visit followed by a SFU Visit 40 days (± 7 days) after the last dose of study medications. Participants who opt not to continue into the Extension Treatment Period will complete a SFU Visit 40 days (± 7 days) after the last dose of study medication.

The Extension Treatment Period consists of in-clinic visits every 12 weeks (± 7 days) and will continue until all participants are withdrawn, until ZLP is approved and available in the US, or until further notice from the Sponsor. During these visits, ZLP accountability and resupply will be performed, medications updated, and safety will be assessed. Participants who withdraw or discontinue ZLP during the Extension Treatment Period will complete a Withdrawal Visit followed by a SFU Visit 40 days (± 7 days) after the last dose of study medication. Participants who transition to commercially available ZLP will complete a Withdrawal Visit but will not require a SFU Visit. If by the time a participant completes the Main Treatment Period ZLP is commercially available, the participant may transition to commercially available ZLP directly following the Week 12 visit at the end of the Main Treatment Period.

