5.4.1 Extent of Exposure

IMP duration will be summarized. The number of days on IMP will be calculated as follows:

$$\text{IMP duration} = [(\text{Date of Last Dose Received}) - (\text{Date of First Dose Received})] + 1$$

The exposure duration (i.e., total time at risk that incorporates 5 half-lives of ZLP) is defined as:

$$\text{Exposure duration (in days)} = [\min (\text{Last dose} + 40 \text{ days}, \text{Last Visit/Contact}) - (\text{Date of First Dose Received})] + 1$$

Patient-years exposure (PEY) will be calculated as the sum of the exposure durations of all study participants divided by 365.25.

The overall extent of exposure in the SS will be summarized during the Main Treatment Period and in the Overall Treatment Period.

Note that temporary drug discontinuations and missed doses will not be incorporated into the calculations of the extent of study drug exposure analyses.

The number of doses missed (from the eCRF Study drug administration page after Day 1) will be summarized cumulatively. The missed doses will be derived based on the expected number of daily doses the participant should receive within a defined period minus the total number of doses he/she has received during that period. For this derivation, the number of total syringes administered to a participant at each visit will be considered via the total number of kits administered at each visit, assuming that each kit contains 7 syringes to be used for 7 daily doses.

In addition to the assessment of study medication duration as a continuous variable, the number and percent of study participants with treatment duration meeting the following criteria will also be summarized:

- ≥ 1 day
- ≥ 8 days
- ≥ 15 days
- ≥ 29 days
- ≥ 57 days
- ≥ 84 days

All drug administration details will be listed.

The compliance between two in-clinic visits, as well as the overall compliance will be described.

The study withdrawal will be summarized over the Main Treatment Period and over the Overall Treatment Period time-to-event, using Kaplan-Meier plot.

For the Main Treatment Period, time to IMP discontinuation is defined as: Date of last IMP dose – date of first IMP dose + 1. Participants that did not early withdraw should be censored at the date of Main Treatment Period completion.

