A TEAE is defined as an AE starting on or after the time of first administration of IMP and up to and including 40 days after the final dose (or last contact depending on which occurs first). Adverse events starting before the date of the first administration of IMP will not be considered TEAEs.

Where dates are missing or partially missing, AEs will be assumed to be treatment-emergent unless evidence exists that does not allow the AE to be treatment-emergent. Handling of missing dates for classification of AEs as TEAEs is described in Section 5.1.1.10.

A TEAE will be counted as a TEAE related to IMP if the response to the question “Relationship to Study Medication” is “Related”.

Severe TEAEs are those with CTCAE Grade 3 or above, or those without a CTCAE grading classified as ‘severe’ by the Investigator.

AEs will be presented as “number of participants (percentage of participants) [number of events]”. In this style of output, “[number of events]” will include all cases of an AE including repeat occurrences in individual participants, while “number of participants” will count each participant only once.

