5.4.2.2 AE summaries

1. A TEAE overview table will be provided by treatment group, including the number, percentage of participants and frequency of the following TEAEs:
 - Any TEAEs
 - Any TEAEs above 5% of occurrence
 - Serious TEAEs
 - TEAEs leading to permanent withdrawal from IMP
 - Treatment-related TEAEs
 - Severe TEAEs
 - TEAEs leading to death
 - All deaths (AEs leading to death)
2. The number, percentage of participants and frequency of the following TEAEs will be summarized by System Organ Class (SOC), high level term (HLT), and PT:
 - Serious TEAEs

- Non-serious TEAEs
- TEAEs leading to death

In case of 5 or less of the following TEAEs, no summary table will be displayed, and the listing of AEs will be used. In case of 6 events or more the number, percentage of participants and frequency of the following TEAEs will be summarized by System Organ Class (SOC), high level term (HLT), and PT:

- Any TEAEs
 - Severe TEAEs
 - TEAEs leading to permanent withdrawal from IMP
 - Treatment-related TEAEs leading to permanent withdrawal from IMP
3. The number, percentage of participants with TEAEs will be summarized by maximum intensity (mild, moderate and severe), SOC, and PT as well as by intensity (mild, moderate and severe), SOC, and PT.
4. The number, percentage of participants and frequency of the following TEAEs will be summarized by relationship, SOC, HLT, and PT:
- Any TEAEs
 - Serious TEAEs
 - Fatal TEAEs

For these summaries, the number and percentage of participants who experienced at least one TEAE as well as the number and percentage of participants who experienced each specific SOC, HLT (if HLT is presented) and PT will be presented. The corresponding number of TEAEs will also be presented for the Overall Summary of TEAEs table. For the presentation of TEAE incidences, the SOCs will be sorted alphabetically, and HLT within SOC – (if HLT is presented), and within HLT, the PT will be used and presented by decreasing total frequency.

Listings of all AEs in (ES), permanent withdrawal of IMP due to AEs, participant discontinuation from study due to AEs, AEs leading to death will be presented by participants in SS.

To assess the impact of the COVID-19 pandemic on safety, additional summaries and listings will be presented. All COVID-19 related TEAEs will be summarized by MedDRA SOC, HLT and PT.

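### Overall Treatment Period adverse events are tabulated without exposure adjustment, although the Extension is optional and open-ended and the SAP already defines patient-years of exposure

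*SAP*

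**What the plan says.** - **Periods.** SAP 5.1.1.1.3.1: "The safety analyses will be performed on the Main Treatment Period as well as on the Overall Treatment Period". The Overall period is the Main plus the Extension Treatment Period. Under SAP 5.7, tables for both are produced at the final analysis.
- **Entry to the Extension.** SAP 1.2: "All study participants who complete the Main Treatment Period will have the option to continue ZLP treatment in the Extension Treatment Period".
- **Length of the Extension.** SAP 1.2 says that it "will continue until all participants are withdrawn, until ZLP is approved and available in the US, or until further notice from the Sponsor".
- **Adverse event display.** SAP 5.4.2.1 sets the format as participants, percentage and, in brackets, the number of events including repeats. SAP 5.4.2.2 asks for "the number and percentage of participants who experienced at least one TEAE as well as" the same figures by SOC, HLT and PT. SAP 5.4.3.1 asks for incidence tables for the AEs of interest.
- **Exposure.** SAP 5.4.1 defines exposure duration as time at risk. It runs from first dose to the earlier of last dose plus 40 days and last visit or contact, which matches the end of the TEAE window in SAP 5.4.2.1. It continues: "Patient-years exposure (PEY) will be calculated as the sum of the exposure durations of all study participants divided by 365.25". Extent of exposure is then summarised for the Main and Overall periods.
- **Protocol.** Section 9.4.1: "Incidence rates for TEAEs will be summarized overall, by maximum severity, and by relationship to study medication". No person-time denominator is named.

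**The concern.** A percentage of participants with an event is easy to interpret when everyone is followed for about the same time. That is broadly so in the Main Treatment Period and is not so in the Overall Treatment Period. There, time at risk depends on when a participant enrolled, whether he or she opted in, and when commercial supply or a sponsor decision ended the Extension. Even among those who do not extend, a participant who moves straight to commercial product needs no safety follow-up visit, so the window can close near Day 84 rather than Day 124.

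The SAP handles unequal follow-up elsewhere: it plans Kaplan-Meier displays for rescue therapy and for study withdrawal. It plans neither a rate nor a time-to-event display for adverse events. At stake is whether the Overall-period tables can be interpreted. A reader who sets them beside the Main-period tables, or beside a study of different length, cannot tell a higher event rate from longer observation.

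**Working it through.** **Does any adverse event output use PEY?** SAP 5.4.2.1, 5.4.2.2 and 5.4.3.1 give counts, percentages and frequencies. PEY is defined only in 5.4.1, where the output is a description of exposure. No section of the SAP divides events or participants by it. The table specifications are a separate document (SAP 1) that was not available, so this is established for the SAP text only.

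**Is there a plan figure to reproduce?** No. Neither document states an expected event rate or Extension duration, so what follows is illustration on assumed values.

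**Inputs**
- Time at risk for a completer who does not extend: Day 84 + 40 days = 124 days (Schedule of Activities; SAP 5.4.1).
- 20 participants (SAP 3).
- Assumed: constant first-event rate λ of 0.5 or 1.0 per patient-year; total time at risk for extenders of 208, 376, 405 or 712 days.

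**Formula.** Expected crude incidence after T days is 1 − exp(−λT/365.25).

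Whole cohort with the same time at risk, λ = 0.5:
- 124 days: 1 − exp(−0.5 × 124/365.25) = 15.6%
- 405 days: 1 − exp(−0.5 × 405/365.25) = 42.6%, a ratio of 42.6/15.6 = 2.7

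The Overall period pools extenders with non-extenders. With 10 at 124 days and 10 at 405 days, the crude figure is (15.6 + 42.6)/2 = 29.1%, a ratio of 29.1/15.6 = 1.9.

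Other mixtures of 20 participants, with non-extenders at 124 days:

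| Scenario | PEY | Crude %, λ = 0.5 | Crude %, λ = 1.0 |
|---|---|---|---|
| nobody extends | 6.8 | 15.6 | 28.8 |
| 10 extend, 208 days in all | 9.1 | 20.2 | 36.1 |
| 10 extend, 376 days in all | 13.7 | 27.9 | 46.5 |
| 16 extend, 376 days in all | 17.8 | 35.3 | 57.2 |
| 16 extend, 712 days in all | 32.6 | 52.9 | 74.4 |

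Within each column the underlying rate is the same. Participants with an event divided by person-time to first event returns 50 or 100 per 100 patient-years in every row, as it must under a constant rate.

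**Precision.** Suppose 6 participants have an event over 12 patient-years to first event, or 50 per 100 patient-years. The exact Poisson limits for a count of 6 are 2.20 and 13.06. Dividing by 12 gives a 95% interval of about 18 to 109 per 100 patient-years.

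**The case against.** The strongest case against is that little in this study rests on these tables. Both primary and both secondary safety endpoints are confined to the Main Treatment Period, where planned treatment is 12 weeks. There is one arm, so no treatment comparison can be biased, and the only planned test is on MG-ADL. The Extension was added to provide access, and no comparison of Overall with Main figures is planned. All of this stands and limits the weight of the point. Still, the sponsor has chosen to tabulate Overall-period safety, and one of the other safety endpoints in Table 1.1, the incidence of TEAEs, carries no period restriction.

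Second, event counts and PEY are both planned, so a reader could divide one by the other. That is true for total events. The participant-based rate needs time to first event, which no planned table gives.

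Third, rates per patient-year assume a roughly constant hazard. If events cluster soon after the switch, long Extension time dilutes the rate. This also stands, and is the reason to show Main and Extension separately.

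A reader might take the protocol's phrase on incidence rates as a promise of person-time rates that the SAP breaks. The documents do not support that: the protocol names no such denominator, and its general rule for categorical data (Section 9.2) is number and percentage.

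**Conclusion.** The gap is real and of moderate weight. For the Overall Treatment Period the SAP reports adverse events as participants, percentages and event counts with no exposure adjustment, over follow-up that is optional and open-ended, while defining a suitable exposure measure that no adverse event summary uses.

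The size is illustrative only. At 0.5 per patient-year, 15.6% at 124 days becomes 42.6% if everyone had 405 days, but 29.1% if only half did. These figures rest on an assumed constant rate and assumed durations.

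Three stronger readings are tempting and do not hold:
- That the primary safety result is compromised. It is confined to the Main Treatment Period.
- That a 2.7-fold distortion should be expected. That figure compares whole cohorts at durations that the documents do not give.
- That exposure adjustment would make Extension data representative. Those data come only from participants who completed 12 weeks and chose to stay, and a rate does not remove that selection.

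**What to change.** Amend SAP 5.4.2.2 and 5.4.3.1. For the Overall-period summaries of any TEAE, serious TEAEs, severe TEAEs, TEAEs leading to withdrawal of IMP, and AEs of interest, add:

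1. events per 100 PEY;
2. participants with an event per 100 patient-years at risk, with time counted to the first event or the end of the exposure window, and an exact Poisson 95% confidence interval.

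Show both rates separately for the Main and Extension Treatment Periods, and state in SAP 5.4.1 how exposure and events are assigned to each. The present exposure formula has no truncation at the end of the Main period for participants who continue. Rates by SOC and PT are optional. Footnote that Extension rates describe participants who completed the Main period and opted in, and that the rates assume a roughly constant hazard within period.

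**Cost.** No new data: the calculation uses event onset, dosing and contact dates. The work is more than one added column, because time to first event and the Main/Extension split are new derivations. Intervals will be wide with 20 participants.

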5.1.1.1.4 Mapping of assessments performed at (Early) Withdrawal Visit

If a participant prematurely discontinues study drug at any time prior to Week 12 during the Main Treatment Period, the participant should return to clinic for a stand-alone EW Visit. If a participant withdrew during the Extension Treatment Period, the participant should perform a Withdrawal Visit. These assessments will be mapped to the next scheduled visit where each assessment is evaluated as per protocol. This approach means that there is a chance that EW (or Withdrawal) data will be mapped to different visits according to the schedule of assessments.

